Investigational Device Description	
Device Name: MedRhythm's MR-Stride Plus
 
The following materials will be provided:
 
 1. Access to Stride Plus patient application. 2. Mobile Devices. 3. Motion Sensors. 4. Headphones. 
The MedRhythms MR-Stride Plus includes a patient application and sensors with commercially available headphones and smartphones. The MR-Stride Plus is a device intended to improve gait metrics and improve walking speed. This technology uses embedded audio cues to facilitate improvements in walking speed based on Rhythmic Auditory Stimulation. When using the system, patients walk with sensors that are attached to their shoes and collect gait parameters, including the following measurements: speed, stride length, symmetry (temporal and spatial), and cadence. The algorithm uses data from the sensors to inform changes made to the audio cues. These cues, which are embedded in time-shifted music, are delivered back to the users who aim to walk to the beat.
 
Research shows that walking to an external rhythmic stimulus globally engages the brain, coupling the auditory and motor regions. For stroke survivors with damage to the motor system, this dual engagement has the effect of establishing new neural connections to the motor region. Furthermore, this has the potential to make walking certain distances, which may ordinarily be onerous or impossible tasks, achievable for these individuals. As a result of neuroplasticity, repeating these audio-cueing exercises on a consistent basis can change one's brain composition, allowing walking improvements made with the device to manifest without the engagement of the intervention.

Enrollment and Consent	Study Participants will be enrolled into the study by a study staff member at participating study sites. Once informed consent is received, Study Participants will be screened for enrollment into the study.
Study Objectives	The purpose of this clinical study is to evaluate the effects of the Stride-Plus on tolerability, biomechanics and walking speed in the acute stroke care setting in addition to its impact on length of stay. The study will also look at the impacts of the intervention on falls and cost of care over a 90-day period post-discharge from acute care setting.

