	
For all Study Participants, standard of care will be followed in both the acute care setting and in the discharge setting. Data required to evaluate the study objectives will be collected from record review and participant interviews. Participants will not be required to physically visit the study facility for study-specific procedures once they have been discharged from the acute care setting. Participants will be contacted by telephone to answer study assessment questions (e.g., mRS) intended at Days 45 (+/-2 Days), and 90 (+/-7 Days).
 
For those Study Participants enrolled into Arm A, study staff will review the intended walking intervention therapy schedule with the study participant. The Stride Plus is intended to be used for thirty (30) minutes a day, three (3) times a week. Participants will complete the following intervention phases related to use of the Stride Plus:
 
Intervention Phase 1 (within 24 hours from admission): In addition to standard of care therapy, study participants will complete at least one (1) walking therapy session with the Stride Plus while an inpatient in the acute care setting. Additional study therapy sessions will continue until the Study Participant is discharged from the acute care setting.
 
Intervention Phase 2 (Day 1 post-discharge to Day 90): In addition to standard of care therapy, study participants will complete a series of three (3) remote walking therapy sessions a week with the Stride Plus following discharge from acute care setting. Participants will schedule their sessions according to their preference and needs. Intervention Phase 2 will continue until the Study Participant is 90 days since discharge or earlier if the study participant is withdrawn from the study therapy. Participants will complete a walking test using the Stride Plus at discontinuation to determine the walking speed.
 
Post-Intervention Phase: Participants will be followed from discontinuation of the Stride Plus until Day 90. At Day 90 (+7 days), participants will complete a walking test using the Stride Plus to determine walking speed.
 
For those study participants in Arm B, the control group, only standard of care therapy will be provided. Participants will complete a 6-meter walk test (approximately 20 feet) to measure gait speed at baseline, biweekly post- discharge from acute care to day 90 (+/-7 days) following discharge.

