Primary Endpoint	
The primary study objectives are as follow:
 
 1) Change in gait speed (m/s) from baseline to study completion (90 days following discharge from acute care or earlier if study participant withdraws); 2) time-to-functional change in gait speed from baseline to study completion 3) adherence to the MR-Stride Plus therapy schedule.
Secondary Endpoint	
The secondary study objective is to assess the median length of stay in acute stroke hospital and the percent of readmission during the 90 (+/-7) days following discharge.

Participant Population	
No age, race, education or geographical restrictions apply. All individuals who meet the inclusion/exclusion criteria at participating study sites will be considered.

Inclusion Criteria	
To be enrolled and randomized into the study, potential Study Participants must meet all of the following inclusion criteria:
 
 1.0 Must be 18 years of age or older. 2.0 Must be able to read and speak English fluently. 3.0 Be within 24 hours from admission for confirmed stroke event.

	
4.0 Currently able to walk at a speed greater or equal to 0.4m/s, but less than 1.0m/s, as determined by a 6-meter walk test (approximately 20 feet) for comfortable walking speed (the average of three trials).
 
5.0 Demonstrates some level of asymmetry in gait.
 
6.0 Is expected to be discharged from the acute care setting requiring physical therapy per standard of care and participant has verbally committed to receiving at least one therapy session.
 
7.0 Able and willing to consent with proposed study schema (verbal commitment), including consent to participate in communication with the treating clinician (as needed) during the study period.
 
8.0 Score ≤1 on question 1b and a 0 on question 1c on the NIH Stroke Scale.
 
9.0 Able to safely participate in protocol-defined walking therapy sessions of 30-minute duration as determined by the Investigator.

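### Arm A can have two end-of-study gait speeds, one from the Stride Plus and one from the 6-meter walk, and the protocol does not say which is the primary value

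*Protocol*

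**What the plan says.** All references are to the protocol.

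- **Primary Endpoint.** The first endpoint is "Change in gait speed (m/s) from baseline to study completion", with completion at 90 days after discharge or at earlier withdrawal. The second is time to functional change in gait speed. Neither names a test or an instrument.
- **Inclusion Criterion 4.0.** The entry speed is given as "Currently able to walk at a speed greater or equal to 0.4m/s, but less than 1.0m/s". It is measured at a comfortable pace on the 6-meter walk, taking the mean of three trials.
- **Study Design, Arm A.** In Intervention Phase 2: "Participants will complete a walking test using the Stride Plus at discontinuation to determine the walking speed". In the Post-Intervention Phase: "At Day 90 (+7 days), participants will complete a walking test using the Stride Plus to determine walking speed".
- **Procedures, Arm A.** Participants withdrawn from therapy are asked to do a device gait-speed assessment at Days 45 and 90 if willing. Separately, the arm has a 6-meter walk at screening and every two weeks until the study ends. A further gait-speed assessment at withdrawal from therapy has no named instrument.
- **Study Design, Arm B.** "Participants will complete a 6-meter walk test (approximately 20 feet) to measure gait speed at baseline", then biweekly to Day 90. Procedures adds walks at Days 45 and 90. No device test is given to this arm.
- **Minimizing Bias.** The trial is open label. Directly after calling gait speed the primary outcome, the row says participants will not learn their 6-meter walk results.
- **Study Duration.** The remote sources for study data, gait speed among them, are medical records, the MR-Stride Plus database and telephone contact.

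**The concern.** The Stride Plus is the treatment under test. The Investigational Device Description says of its audio: "These cues, which are embedded in time-shifted music, are delivered back to the users who aim to walk to the beat". It separately claims a lasting effect, "allowing walking improvements made with the device to manifest without the engagement of the intervention". A speed recorded while the cues play and a speed recorded without them answer different questions, and the protocol does not say whether the cues are on during a Stride Plus walking test.

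If the device reading becomes Arm A's final value, three things follow:

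- Instrument is confounded with arm. Any systematic difference between the device and the 6-meter walk, and any immediate effect of the cues, passes in full into the between-arm difference.
- Arm A's change runs from a 6-meter entry test to a device reading, while Arm B's change stays on one instrument. Subtracting or adjusting for a 6-meter baseline does not remove the offset, and neither does randomization.
- A cued reading would not test the carry-over claim.

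If the 6-meter walk is used in both arms, none of this arises.

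**Working it through.** **Step 1. Can both Arm A values occur?** Yes. The Phase 2 device test is tied to discontinuation, and Phase 2 runs to 90 days or to earlier withdrawal, so it reaches participants treated to the end as well as early stoppers. The biweekly 6-meter walk runs over the same period. Set side by side:

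| Time | Arm A | Arm B |
|---|---|---|
| Entry | 6-meter walk | 6-meter walk |
| Follow-up | 6-meter walk biweekly; device at Day 45 if withdrawn from therapy and willing | 6-meter walk biweekly and at Day 45 |
| Therapy stops | Device (Study Design); instrument not named (Procedures, for withdrawal before Day 90) | not applicable |
| End of study | Device, and last biweekly 6-meter walk | 6-meter walk at Day 90 |

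No sentence ranks the two Arm A values.

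**Step 2. What size could matter?** The protocol states no alpha, power, SD, effect size or instrument offset, so there is no figure to reproduce and what follows is an illustration.

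Inputs from the protocol: about 20 per arm; entry speeds from 0.4 to just under 1.0 m/s.

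Assumed: two-sided 5% two-sample t-test; SD of change 0.15, 0.20 or 0.25 m/s; a constant offset *b* in every Arm A final value and in no Arm B value.

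Scale of the offset: 5% of 0.4 and of 1.0 m/s is 0.02 and 0.05 m/s; 10% is 0.04 and 0.10 m/s. At a mid-range speed of 0.7 m/s, 5% and 10% are 0.035 and 0.07 m/s.

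Formula: noncentrality = *b* / (SD × √(2/20)), with √(2/20) = 0.316, 38 degrees of freedom and critical value 2.024. For *b* = 0.05 and SD = 0.20, this is 0.05 / (0.20 × 0.316) = 0.79, and the rejection rate is 12.0%.

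False-positive rate with no true effect:

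| Offset (m/s) | SD 0.15 | SD 0.20 | SD 0.25 |
|---|---|---|---|
| 0 | 5.0% | 5.0% | 5.0% |
| 0.02 | 7.0% | 6.1% | 5.7% |
| 0.035 | 11.1% | 8.4% | 7.2% |
| 0.04 | 13.0% | 9.5% | 7.8% |
| 0.05 | 17.7% | 12.0% | 9.5% |
| 0.07 | 30.1% | 19.0% | 13.9% |
| 0.10 | 53.8% | 33.8% | 23.4% |

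**Step 3. An offset of the other sign.** With an assumed true effect of 0.15 m/s, a negative offset leaves an apparent effect of 0.15 − 0.02 = 0.13 or 0.15 − 0.05 = 0.10 m/s:

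| Offset (m/s) | Power, SD 0.15 | SD 0.20 | SD 0.25 |
|---|---|---|---|
| 0 | 86.9% | 63.7% | 45.6% |
| −0.02 | 76.1% | 51.7% | 36.1% |
| −0.05 | 53.8% | 33.8% | 23.4% |

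If only a fraction of Arm A values come from the device, the mean bias is that fraction of *b*.

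**Step 4. Does the biweekly walk already supply a Day 90 value in Arm A?** Not under every reading. Taking biweekly as every 14 days:

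- Counted from discharge, the walks fall on Days 14, 28, 42, 56, 70 and 84, and the last lies inside Days 83-97.
- Run to the end of the ±7-day window, some walk always falls in Days 83-97.
- Counted from screening and stopped at Day 90, with discharge *d* days after screening, the last walk is the largest multiple of 14 not above 90 + *d*, minus *d*. For *d* = 2 this is 84 − 2 = Day 82; for *d* = 7 it is 84 − 7 = Day 77. For an assumed *d* of 2-7 days, the last walk therefore precedes the window.

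Procedures names a Day 90 walk for Arm B but not for Arm A, so the Arm A walk should be named too.

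**The case against.** The strongest reply is that the text already points to the 6-meter walk and an analysis plan could settle the rest. That walk is the entry test and the only test given to both arms. Its Arm A schedule runs to study completion, the same end point as the primary endpoint, and the Minimizing Bias row pairs it with the primary outcome. This makes the 6-meter walk the more natural reading, but it remains inference. Procedures also uses the term gait speed for the device assessment after withdrawal from therapy, and Study Duration lists the device database as a remote data source at a stage when participants need not return to the site. An analysis plan could choose between two readings, but it could not fix afterwards whether cues were on during a test.

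Four narrower points have some force:

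- The Day 90 device sentence sits in the Post-Intervention Phase and may cover only those who stop early. The Phase 2 discontinuation test still reaches completers.
- A Stride Plus walking test might be a 6-meter walk recorded by the shoe sensors. The text does not say so, and a sensor offset and the cue question would remain.
- The carry-over claim does not prove that cued and uncued speeds differ numerically. That is right: they are different by definition, and the size of any difference is unknown.
- An offset of 0.10 m/s is 10% of the upper limit of the entry range, so a 10% discrepancy at entry speeds could not average that much. At 0.7 m/s it is 0.07 m/s, giving 13.9-30.1%. The 0.10 row is an outer bound.

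**Conclusion.** The concern holds and should be fixed. It is not a contradiction, since both Arm A schedules can be carried out. The defect is that two of the three primary endpoints have no named instrument while the protocol prescribes a second end-of-study measurement in one arm only, made with the treatment device under unstated cue conditions.

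The omission is certain; the harm is conditional. It is nil if the 6-meter walk is analysed in both arms. If every Arm A endpoint is a device reading, then under the assumptions above a 5% discrepancy over the entry range (0.02-0.05 m/s) puts the nominal 5% error at between 5.7% and 17.7%. A discrepancy against the device of the same size cuts power for an assumed 0.15 m/s effect from 46-87% to 36-76% (at −0.02) or 23-54% (at −0.05). The SDs, offsets, true effect, test and full use of the device reading are all assumptions; none comes from the protocol.

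**What to change.** - In Primary Endpoint, state that the two gait-speed endpoints use only the 6-meter walk, done under the same conditions and without device audio, in both arms at baseline and every follow-up.
- In Procedures, Arm A, name a Day 90 6-meter walk as is done for Arm B, and state that the walks continue for participants withdrawn from therapy. Name the 6-meter walk as the instrument for the assessment at withdrawal.
- In Study Design and Procedures, label every Stride Plus walking test as supplementary Arm A data outside the between-arm comparison, and state whether cues are on.
- Reconcile the two sections accordingly, including the Day 90 window, which is +7 days for the device test and ±7 days elsewhere.

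The cost is low: the biweekly 6-meter walk is already scheduled in both arms, so this is mainly a change of wording. The device reading loses any endpoint role. The real work is to have the walk done the same way in both arms after discharge, when participants need not attend the site, and the protocol should say how.

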Procedures	
ARM A: STANDARD OF CARE + MR-STRIDE PLUS
 
For Study Participants randomized into Arm A, therapy sessions will begin within twenty-four (24) hours of enrollment. Intervention Phase 1 of the study requires a minimum of one (1) therapy session with the possibility of additional sessions until discharge; however, no more than 3 therapy sessions should occur during a given week. Intervention Phase 2 of the study requires 3 independent, remote therapy sessions a week regardless of discharge setting (e.g., rehabilitation hospital or home). Therapy will continue until day 90 (+/-7) following discharge from acute care. Therapy sessions with the MR-Stride Plus should not replace standard of care physical therapy, but be used in addition to standard of care physical therapy.
 
Participants may be contacted by the study staff to collect data on the number of standard of care physical therapy services provided and occurrence of readmission to acute care.
 
Participants will be able to schedule their three (3) sessions a week therapy according to their needs. Participants will be allowed to miss sessions if they are unable to make them up on a different day in the week. Participants therapy activity will be monitored remotely by the study team. If participants are unable to maintain the therapy schedule, the study will contact the participants to gauge willingness to continue. At investigator discretion and participant agreement, the number of sessions a week may be reduced or the participant may withdraw from therapy. If the participant is withdrawn from therapy, participants will be asked if they are willing to participate in a gait speed assessment using the MR-Stride Plus at day 45 and 90 post-discharge if they have not already been completed.
 
The 6-meter walk test (approximately 20 feet) will be conducted to evaluate gait speed at screening and biweekly thereafter until study completion. Gait speed will also be assessed at

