	
the time of withdrawal from study therapy if withdrawal occurs before Day 90 (+/-7) post discharge.
 
At the initial therapy session, Study Participants will be provided with all necessary equipment (pre set-up) and instruction for using the MR-Stride Plus. Study staff will provide appropriate oversight of the Participant during their initial walking therapy session in acute care to ensure safety; study staff will not be required to provide any instruction on use of the device. Participants will conduct 30 minutes of walking therapy at the participant's self-selected pace in a space (e.g., track or hallway) that limits the amount of stops and/or pivot turns in order to optimize velocity. Participants may choose to take breaks as needed, or when investigators believe that a rest break is necessary. The use of an overhead harness system is prohibited in this study. If technical or medical issues arise, the training session should be terminated to allow for adequate resolution.
 
For independent, remote therapy sessions following discharge from the acute care hospital, it is not required that a participant be under the supervision of clinical staff or a caregiver (depending on discharge setting), but participants may choose to according to their preference. Participants should perform their therapy sessions in an environment that limits safety hazards and, in a space, e.g., track or hallway, that limits the amount of stops and/or pivot turns in order to optimize velocity. Participants will perform their 30 minutes of walking therapy at their self-selected pace.
 
MR-Stride Plus Procedure: Study staff and participants will be required to follow the Instructions For Use (IFU) provided by MedRhythms. The IFU will detail all procedures required for proper operation of the system. Study Participants will be trained in utilizing the Stride Plus by the study staff. Mobile devices that have the MedRhythms Stride Plus application installed will be provided for use during therapy sessions. Participants will be provided with a pre-established username and password. No personally identifiable patient information will be recorded or stored in the Stride Plus application.
 
ARM B: STANDARD OF CARE
 
For Study Participants randomized into Arm B, clinical standard of care will be followed with no intervention provided using the MR-Stride Plus. Participants will also complete the 6MWT at screening, baseline and biweekly post-discharge from acute care and at days 45 and 90 (+/-7 days) following discharge.
 
All participants will be followed for 90 days following discharge from acute care facility for initial stroke event and discharge date, discharge setting, number of physical therapy services and occurrence of readmission to acute care will be collected.

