Minimizing Bias	The study is not blinded because the primary outcome measure of gait speed renders the likelihood of a placebo benefit unlikely. However, Study Participants will be blinded to the results of the 6-meter walk test (approximately 20 feet). No results will be provided to the Study Participant at any time during participation in the trial.
Study Visits	All key assessments will be conducted at the study site and remotely via telecommunication, as applicable.
Study Duration	Each Participant is required to complete a screening visit. For Participants who are randomized into Arm A (MR-Stride Plus Intervention), therapy sessions will take approximately forty-five (45) minutes for set-up and therapy. After the first therapy session in

	
the acute care setting, participants should be able to complete the setup and therapy session with the MR-Stride Plus independently. Collection of data related to study adherence (for participants in the MR-Stride Plus Intervention), gait speed assessment, standard of care administration, discharge and readmission will be performed by study staff remotely through review of medical records, MR-Stride Plus database, and by contacting the participant over the phone. Once participants have reached 90 days following discharge from the acute care facility for the initial stroke event, no follow-up or subsequent Participant involvement is required.

Study Discontinuation, Drop Out, Withdrawal and Replacement	
Participants may discontinue their participation in the study at any time. A Participant may be withdrawn from the study at any time at the discretion of the Investigator.
 
Participants who are withdrawn or drop out prior to the study endpoint will still have data that was collected up until the withdrawal/drop out eligible for analysis. These Participants will be analyzed in an Intent-To-Treat analysis.

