Data Analysis	UMass Memorial Health Care will be responsible for data analysis. Intent to treat: All Study Participants that enrolled in the study, regardless of withdrawal or incomplete data (if analysis can be made)

Confidentiality	
The Principal Investigator and designees, employees, and agents involved with this study will comply with relevant state and federal laws relating to the confidentiality, privacy and security of Participant's health information. They will only create, maintain, use or disclose any data that is generated by this study or other information disclosed to the Principal Investigator or their employees or agents during the course of the study to MedRhythms, Institutional Review Board, Regulatory Authority or other authorized recipients as appropriate for the execution, analysis, review and reporting of this study. Such information shall not be used for any other purposes and will remain confidential.
 
Study Participants will be informed that all data collected for study purposes will be held in strict confidence and used for research purposes only. Records may be paper or electronic. Privacy of participants will be protected by conducting all in-person interactions in a semi-private or private space within the rehabilitation laboratories. No personally identifiable information will be discussed in common areas.
 
Paper Documents
 
Will be stored in a locked file cabinet that only the study staff has access to. Study Participant files may also be scanned and stored on a secure, password-protected server authorized to store restricted data, with access provided only to the PI and key study staff.
 
Codified Study Participant Identification Number
 
Data collected during this research will be labeled using a codified participant identification number.
 
Research Data
 
Data collected specifically for the study will be labeled with the applicable Study Participant ID and stored on a secure, password-protected server. Data may be transferred as a local copy to password-protected study staff computers for processing or to prepare media material for publications, presentations or training purposes.
 
System Data
 
The MR-Stride Plus device will collect and store data related to the platform's performance on a secured cloud-based drive owned by MedRhythm's. Personally identifiable information will not be collected by the platform or stored by the company. Only the PI and designated study staff will have access to the data collected under this protocol. The PI and all study staff will have access to all coded data housed on a password-protected secured network drive.

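### Primary endpoint 1 ends at Day 90 or at an earlier withdrawal, so an early gait speed meets the same definition as a Day 90 speed

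*Protocol*

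**What the plan says.** **Endpoint.** Primary Endpoint, item 1, is change in gait speed "from baseline to study completion (90 days following discharge from acute care or earlier if study participant withdraws". No minimum follow-up is set.

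**Analysis of those who leave.** The section on discontinuation, drop-out and withdrawal describes these participants as leaving before the study endpoint, makes "data that was collected up until the withdrawal/drop out eligible for analysis", and places them in the intent-to-treat analysis. Data Analysis includes "All Study Participants that enrolled in the study, regardless of withdrawal or incomplete data (if analysis can be made".

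**Stopping the device.** Elsewhere the protocol names therapy when it means therapy. Under Study Design, Phase 2 runs to 90 days after discharge or "earlier if the study participant is withdrawn from the study therapy". Under Procedures, Arm A, gait speed is also taken at "the time of withdrawal from study therapy if withdrawal occurs before Day 90". No gait test at withdrawal is described for Arm B, or for a participant of either arm who leaves the study itself.

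**Gait tests up to Day 90.**
- Arm B has the 6-meter test at baseline and biweekly to Day 90 (Study Design). Procedures, Arm B, also lists days 45 and 90, under an abbreviation read here as the same test.
- Arm A has the 6-meter test "at screening and biweekly thereafter until study completion". Its Day 90 test is described differently: in the Post-Intervention Phase "participants will complete a walking test using the Stride Plus to determine walking speed", and for those who have stopped the device "participants will be asked if they are willing to participate in a gait speed assessment using the MR-Stride Plus at day 45 and 90".

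**The concern.** An endpoint needs one time point. Here the end differs by participant, and an early speed is not an incomplete observation of the endpoint: under the stated definition it is the endpoint. An analysis plan that treated Day 90 as missing for such a participant would depart from the Primary Endpoint section, so this is more than a missing-data detail left for later.

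Timing matters because participants enter within 24 hours of admission and both arms receive standard-of-care therapy. Speed is likely to change over the next 90 days whether or not the device works. An arm that loses more people, or loses them sooner, then contributes more speeds from early in recovery, and the arm difference partly reflects time since stroke. Unequal withdrawal is plausible: the study is unblinded, and only Arm A carries an additional programme of three sessions a week, which Procedures expects some participants to be unable to maintain.

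**Working it through.** The protocol states no withdrawal rate, recovery curve, SD or power calculation, so there is no figure of its own to reproduce. What follows is an illustration.

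**From the protocol:** about 40 participants, expected 20/20 (Study Design); endpoint at Day 90 after discharge.

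**Assumed:**
- no device effect, and withdrawers recover like everyone else;
- natural gain by Day 90, G = 0.10 to 0.30 m/s;
- s, the share of that gain made before discharge, 0 or 0.5;
- w, the day after discharge of the early speed, 14, 30 or 45;
- f(w), the share of the post-discharge gain reached by day w: linear, w/90, or front-loaded with a 30-day time constant, (1 − exp(−w/30)) / (1 − exp(−3)).

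| w | f linear | f front-loaded |
|---|---|---|
| 14 | 0.156 | 0.392 |
| 30 | 0.333 | 0.665 |
| 45 | 0.500 | 0.818 |

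**Formula.** If the early speed is taken as the endpoint value, each withdrawer falls short by G × (1 − s) × (1 − f(w)). The bias, Arm A minus Arm B, is

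−(pA − pB) × G × (1 − s) × (1 − f(w)),

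where pA and pB are the proportions withdrawing.

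**30% v 10% (6 v 2 of 20), s = 0:**
- day 14: 0.20 × 0.10 × 0.608 = 0.012 to 0.20 × 0.30 × 0.844 = 0.051;
- day 30: 0.20 × 0.10 × 0.335 = 0.007 to 0.20 × 0.30 × 0.667 = 0.040;
- day 45: 0.20 × 0.10 × 0.182 = 0.004 to 0.20 × 0.30 × 0.500 = 0.030.

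All are against Arm A. With s = 0.5 each is halved, so the whole range is 0.002 to 0.051 m/s. At 10% v 30% the sign reverses.

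**20% v 15% (4 v 3 of 20), s = 0:** 0.05 × 0.10 × 0.182 = 0.001 to 0.05 × 0.30 × 0.844 = 0.013.

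**20% in both arms:** with the same timing, 0. With Arm A at day 14 and Arm B at day 45, the bias is −0.20 × G × (1 − s) × (f(45) − f(14)). At s = 0 this runs from 0.20 × 0.10 × 0.344 = 0.007 to 0.20 × 0.30 × 0.425 = 0.026 against Arm A, and half of that at s = 0.5.

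**Scale.** The standard error of the arm difference is SD × √(2/20): 0.038 at an assumed SD of 0.12, 0.057 at 0.18 and 0.079 at 0.25. The largest 30% v 10% value, 0.0507, is 0.9 standard errors at SD 0.18, and 1.3 and 0.6 at the two ends of the SD range. The largest 20% v 15% value, 0.0127, is 0.2 standard errors at SD 0.18.

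**The case against.** **The sections can be read together harmlessly.** The withdrawal section speaks of people leaving before the study endpoint and only makes their data eligible. It does not say that the last speed stands in for Day 90. On that reading follow-up ends at Day 90 or at exit, and whatever was collected is used. This stands in part: it is a possible intention, and it shows that the protocol disagrees with itself. It does not remove the clause in the Primary Endpoint section, which followed literally makes the early value the endpoint.

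**The model for missing values belongs in the SAP.** Agreed; the repeated-measures model below is an example only. The time point of a primary endpoint is a protocol matter.

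**The size is assumed, and small in most scenarios.** Agreed. It is zero under equal rate and timing.

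**Stronger readings that a reader might infer:**
- *That withdrawal means stopping the device, so the early cut-off falls on Arm A alone and displaces a planned Day 90 speed.* The only withdrawal-time gait tests are indeed for therapy withdrawal. But the protocol says therapy where it means therapy, so leaving the study is the natural reading, and the Post-Intervention Phase keeps those who stop the device in follow-up to Day 90. The ambiguity deserves a clarifying sentence; it does not support a size.
- *That a Day 90 6-meter test is already planned in both arms.* It is stated explicitly only for Arm B. Arm A's Day 90 test uses the device, and its 6-meter series runs to study completion, the very term that may end early.
- *That a true device effect is diluted even when withdrawal is equal.* That depends on how such an effect builds up over time, on which the protocol says nothing.
- *That a mandatory Day 90 test conflicts with one that participants are asked to accept.* Participation is voluntary throughout, so this is a matter of wording.

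**Conclusion.** The point holds as a badly fixed endpoint definition. As written, primary endpoint 1 mixes speeds from different times after stroke, and it does not fit the protocol's own description of those who leave. Bias under the null requires that speed changes over follow-up, that early speeds are used as endpoint values, and that withdrawal rate or timing differs by arm. None of the sizes can be found from the protocol. Under the stated assumptions the bias is about 0.002 to 0.051 m/s at 30% v 10%, below one standard error at SD 0.18 (its largest value exceeds one only towards the lower end of the assumed SD range), and at most 0.013 m/s at 20% v 15%. Its direction follows whichever arm leaves more or sooner.

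Severity is minor to moderate: the expected distortion is modest, but the correction to the definition is a matter of wording. The point is confined to endpoint 1. Endpoint 2 uses the same study-completion term, but early exit there can be handled as censoring.

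**What to change.** 1. Define endpoint 1 as change from baseline to gait speed at Day 90 (+/-7) after discharge, for all randomised participants regardless of therapy discontinuation, and delete the clause that allows an earlier end at withdrawal.
2. State that stopping the device therapy is not withdrawal from the study, and that gait testing continues to Day 90.
3. Treat earlier speeds as data preceding a missing Day 90 value, not as the endpoint value. One way is a repeated-measures model on the biweekly speeds that estimates the Day 90 difference; its details can go in the SAP.
4. Reconcile Study Design and Procedures so that Arm A's biweekly 6-meter series explicitly runs to Day 90 and both arms are measured the same way.

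**Cost.** Items 1 to 3 need wording only. Item 4 may add a 6-meter test at Day 90 for Arm A if one is not already intended. Participants who leave the study will still lack Day 90 values, and the repeated-measures model assumes that these are missing at random. The change gives everyone the same target time point; it does not recover data that were never collected.
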